3.1 Inclusion criteria

- Pathologically proven (either histologic or cytologic) diagnosis of Stage IIIA or IIIB non-small cell lung cancer; [according to AJCC Staging, 7th edition; see Appendix G] within 6 weeks of registration. The patient should have histologically or cytologically confirmed N2 disease.
- Activating mutation in *EGFR*
- No prior chemotherapy or radiation for lung cancer.
- Patients may be potentially resectable or unresectable.
- Stage III A or B disease, including no distant metastases- based on following diagnostic workup:
 - History/physical examination prior to registration.
 - CT Scan of the chest or PET Scan within 28 days of study entry
 - CT Scan of abdomen or MRI of abdomen or Pet Scan within 28 days of study entry
 - An MRI of the brain or Head CT Scan with contrast within 28 days of study entry
 - PET scan within 28 days of study entry
 - Mediastinoscopies are highly recommended.
- Patients must have measurable or evaluable disease.
- ECOG Performance Status 0-2.
- Age \geq 18.
- CBC/differential obtained within 2 weeks prior to registration on study, with adequate bone marrow function defined as follows:
 - Absolute neutrophil count (ANC) \geq 1,500 cells/ul
 - Platelets \geq 100,000 cells/ul
 - Hemoglobin \geq 9.0 g/dl (Note: The use of transfusion or other intervention to achieve Hgb \geq g/dl is acceptable.)
 - Serum creatinine \leq 1.5 x ULN
 - Total bilirubin $<$ 2.0 times the institutional Upper Limit of Normal (ULN)
 - AST and ALT \leq 2.5 x the ULN
 - Women of childbearing potential must have:

- A negative serum or urine pregnancy test (sensitivity $\leq 25\text{IU HCG/L}$) within 72 hours prior to the start of study drug administration
- Persons of reproductive potential must agree to use and utilize an adequate method of contraception throughout treatment and for at least 4 weeks after study drug is stopped prior to study enrollment, women of childbearing potential must be advised of the importance of avoiding pregnancy during trial participation and the potential risk factors for an unintentional pregnancy.
- Ability to take oral medication
- Patient must sign study specific informed consent prior to study entry.

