3.2 Exclusion Criteria

- Pleural or pericardial effusion
 - Pleural effusions allowed if one of the following conditions are met: 1) Negative cytology after adequate sampling by thoracentesis 2) Effusion seen on CT scan but not on chest x-ray and deemed too small to tap under CT or ultrasound guidance
- Severe, active co-morbidity, defined as follows:
 - Cardiac Symptoms; any of the following should be considered for exclusion:
 - Uncontrolled angina, congestive heart failure or MI within (6 months)
 - Diagnosed congenital long QT syndrome
 - Any history of clinically significant ventricular arrhythmias (such as ventricular tachycardia, ventricular fibrillation, or Torsades de pointes)
 - Prolonged QTc interval on pre-entry electrocardiogram (> 450 msec)
 - History of significant bleeding disorder unrelated to cancer, including:
 - Diagnosed congenital bleeding disorders (e.g., von Willebrand's disease)
 - Diagnosed acquired bleeding disorder within one year (e.g., acquired anti-factor VIII antibodies)
 - Ongoing or recent (≤ 3 months) significant gastrointestinal bleeding
- Prisoners or subjects who are compulsorily detained (involuntarily incarcerated) for treatment of either a psychiatric or physical (e.g., infectious) illness
- Men and Women who:
 - are unwilling or unable to use an acceptable method to avoid pregnancy for the entire study period and for at least 4 weeks after cessation of study drug, or Women who:

- have a positive pregnancy test at baseline, or
- are pregnant or breastfeeding

4.0 TREATMENT:

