Human IFN- γ ELISA: We will collect 5 ml of peripheral blood using citrate, EDTA, or heparin as anticoagulant from the patients before and 2 weeks after treatment. Plasma will be collected by centrifuging the blood for 10 minutes at 1000 x g within 20 minutes of collection. The plasma will be stored at $\leq 20^{\circ}\text{C}$ or shipped on dry ice. We will analyze the patient plasma samples for in vitro T-cell function by ELISPOT assay using tumor specific antigens. A positive interferon gamma (IFN- γ) response to a common antigen (such as whole influenza virus or EBV) will be used as a control. The results will be correlated to the skin changes and clinical outcome of the patients.

9.0 PATIENT REGISTRATION:

All patients will be registered through the Clinical Trials Office at Montefiore Medical Center ([contact]) Monday through Friday 9:00am – 5:00pm Eastern Standard Time. Eligibility Checklist and Registration Form with supporting documentation, and the signed Patient Consent Form must be emailed to the clinical trials office at Montefiore Medical Center, [contact] , at the time of registration and prior to patient treatment. Please copy the Montefiore Study and Regulatory Coordinator on this email, as well as the Principal Investigator at Montefiore. E-mail addresses are available at the cover sheet of this protocol document.

[figure not shown]
At the time of registration, all eligibility criteria must be checked. Patients must meet all of the eligibility requirements listed in Appendix B (Eligibility Checklist) (Section 3.0). Patients must not start protocol treatment prior to registration.

It is the treating physician's responsibility to review all data submitted to the Clinical Trials Office for accuracy and completeness and he/she must sign the off study form.

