APPENDIX B
ELIGIBILITY CHECKLIST FOR PATIENT REGISTRATION

**EValuation of Erlotinib as a Neoadjuvant Therapy in stage III NSCLC patients
with EGFR mutations (EVENT trial)**

Eligibility Criteria: The answers to the following questions must be **YES** **NO** **N/A**
'**yes**' in order for the patient to be eligible. N/A should only be
answered if description within question allows.

INCLUSION CRITERIA

Pathologically proven (either histologic or cytologic) diagnosis of Stage IIIA or IIIB non-small cell lung cancer [according to AJCC Staging, 7th edition; see Appendix E] within 4 weeks of registration.
 
State Method of Dx: _____ State Date Dx: _____
 
State Stage and TNM: _____ Stage _____ T ___ N ___ M0
			

Activating mutation in EGFR oncogene: check appropriate: exon 19 deletion _____ exon 21 mutation _____ others _____ (specify _____)
			

No prior chemotherapy or radiation for lung cancer
			

Patients may be potentially resectable or unresectable: check appropriate: resectable _____ unresectable _____
			

Mediastinoscopies or EUS/EBUS to evaluate N3 disease. (Please complete the below) Mediastinoscopy: Yes: _____ No: _____ Date (if yes) _____
 
Endoscopic ultrasound (EUS) : Yes: _____ No: _____ Date (if yes) _____
 
Endobronchial ultrasound (EBUS) : Yes: _____ No: _____ Date (if yes) _____
 
Pathological confirmation of N3 nodes: Yes _____ date: _____ No _____
			

Stage III A or B disease, including no distant metastases- based on following diagnostic workup:
			

Eligibility Criteria: The answers to the following questions must be **YES NO N/A**
'yes' in order for the patient to be eligible. N/A should only be answered if description within question allows.

INCLUSION CRITERIA

History/physical examination prior to registration. Date: _____			
CT Scan of the chest or PET/CT Scan within 28 days of study entry Date: _____ State Method: _____			
CT Scan or MRI of abdomen or PET Scan within 28 days of study entry Date: _____ State Method: _____			
An MRI of the brain or Head CT Scan with contrast within 28 days of study entry Date: _____ State Method: _____			
PFT's: Must be done within 8 weeks of study entry. Date: _____			
EKG: Must be done within 6 weeks of study entry. Date: _____			
Patient must have measurable or evaluable disease.			
ECOG performance status 0-2, ECOG PS (0-2): Numerical Value _____			
State age in years _____ Date of Birth _____			

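### The registration checklist (Appendix B) conflicts with Section 3; its missing N2 item, with a clearance definition that sets no baseline condition, could let a patient without N2 disease count as cleared

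*Combined protocol and SAP*

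**What the plan says.** Section 9.0 states "At the time of registration, all eligibility criteria must be checked" and then "Patients must meet all of the eligibility requirements listed in Appendix B (Eligibility Checklist) (Section 3.0". The checklist therefore governs registration, but the same sentence also cites Section 3.0.

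**Nodal status.** Section 3.1 says "The patient should have histologically or cytologically confirmed N2 disease". The nodal line of Appendix B reads "Mediastinoscopies or EUS/EBUS to evaluate N3 disease", and its only nodal pathology field is "Pathological confirmation of N3 nodes", with both yes and no offered. The form has a free entry for stage and TNM, but no line requires N2 or its confirmation.

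**Diagnosis window.** Section 3.1 has "within 6 weeks of registration"; Appendix B has "within 4 weeks of registration".

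**Exclusions.** Appendix B carries only an inclusion heading. Section 3.2 lists effusion, cardiac conditions (among them "Prolonged QTc interval on pre-entry electrocardiogram"), bleeding disorders, detention and breastfeeding, and none of these has an item. The EKG line asks only for a date. A negative pregnancy test and agreement to contraception are on the form.

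**Endpoint.** Section 18.1 defines mediastinal nodal clearance as negative N2 on pathology, in the final resection specimen or at mediastinoscopy. It does not require that N2 was positive before treatment. It also applies intent-to-treat to all primary and secondary analyses. Section 18.5 limits response assessment to treated patients who meet the eligibility criteria.

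**The concern.** Nodal clearance has meaning only in a patient whose mediastinal nodes were involved at the start. Appendix F places T3N1, T4N0 and T4N1 in stage IIIA, so a stage III patient need not have N2 disease. Such a patient can satisfy every line of Appendix B. If later found N2-negative at surgery or restaging, that patient meets the 18.1 definition with no drug effect on the mediastinum. This pushes the primary rate upward and makes both decision boundaries in 18.2 easier to cross.

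The other two mismatches have different consequences. The missing exclusions are a screening gap: a site could complete the form correctly without being asked about effusion, QTc or bleeding. The two windows contradict each other: a patient diagnosed five weeks before registration satisfies 3.1 and fails the form.

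**Working it through.** **Inputs from 18.2.** Null rate 15%, alternative 30%; 19 patients in stage 1, stop at 3 or fewer clearances; 36 more patients; 12 or fewer of 55 means no further study. The plan states type I error 0.05, power 80%, and early stopping 68.4% at 15% and 13.3% at 30%.

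**Formula.** With X ~ Bin(19, p) and Y ~ Bin(36, p):

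- P(early stop) = P(X ≤ 3)
- P(go) = Σ over x = 4 to 19 of P(X = x) · P(Y ≥ 13 − x)

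**The plan's figures reproduce.** At p = 0.15, early stop is 0.684 and P(go) is 0.0477. At p = 0.30, early stop is 0.133 and P(go) is 0.8006.

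**Patients without baseline N2.** Let f be their share and q the probability that such a patient is scored as cleared. If the true clearance rate in N2-positive patients is 15%, the rate the trial observes is

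p = 0.15(1 − f) + q·f,

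an upward bias of f(q − 0.15). Neither f nor q is in the documents; both are assumptions. A q below 1 is reasonable because clearance needs pathology, and under 4.1 and 4.2 patients who progress leave the study and need no mediastinal restaging.

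| f | q | p | Bias (points) | P(go), true 15% |
|---|---|---|---|---|
| 0 | – | 0.150 | 0 | 0.048 |
| 2% | 1.0 | 0.147 + 0.020 = 0.1670 | 1.7 | 0.094 |
| 5% | 1.0 | 0.1425 + 0.050 = 0.1925 | 4.25 | 0.204 |
| 10% | 1.0 | 0.135 + 0.100 = 0.2350 | 8.5 | 0.460 |
| 2% | 0.6 | 0.147 + 0.012 = 0.1590 | 0.9 | 0.070 |
| 5% | 0.6 | 0.1425 + 0.030 = 0.1725 | 2.25 | 0.114 |
| 10% | 0.6 | 0.135 + 0.060 = 0.1950 | 4.5 | 0.217 |

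**By count.** Take a fixed number of such patients among the 55, all scored as cleared and split at random between the stages (hypergeometric). P(go) at a true 15% is 0.081 with one, 0.130 with two, 0.199 with three and 0.397 with five.

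**Which parts enter this calculation.** Only the N2 item and the 18.1 definition do. An unchecked exclusion or a shorter window does not by itself turn an N2-negative specimen into a false clearance.

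**The case against.** The strongest reply is that the form fails to prompt for N2 but does not waive it. Section 9.0 cites Section 3.0 and asks for all criteria to be checked, so 3.1 and 3.2 remain in force. Stage and TNM must be written on the form, so an N0 or N1 entry would be visible. Appendix B lists pathology, mediastinoscopy and EUS/EBUS reports for submission. Section 12.4 provides eligibility review at registration for participating sites and an audit of each patient within 8 weeks. Section 4.2.3 presumes a station that was positive at earlier mediastinoscopy. All of this stands, and it makes large shares such as 10% (5.5 of 55) hard to picture. It does not close the gap: 3.1 is worded as should, baseline mediastinoscopy is advised rather than required, and the reports may be marked as not enclosed or not applicable.

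A reader might infer that the form drops every exclusion. It does not: pregnancy and contraception are covered, and effusion is covered in part, because the form requires M0 and Appendix F makes malignant effusion M1a.

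A reader might also infer that such patients are certain to be counted. That is unsettled. Intent-to-treat in 18.1 keeps them in; 18.5, if it governs the nodal endpoint (18.2 does call clearances responses), leaves them out.

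**Conclusion.** The conflict between Appendix B and Section 3 is real, and it has three separate parts. The N2 gap, together with the 18.1 definition, allows upward bias in the primary rate. The missing exclusions are a screening gap. The 4-week and 6-week windows are a contradiction.

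The size of the bias cannot be determined from the documents. Under assumed shares of 2% to 10%, the false-go probability at a true 15% lies between 7.0% and 21.7% if 60% of such patients count as cleared, and between 9.4% and 46.0% if all do, against 4.8% by design. Every scenario exceeds the stated 0.05, and one such patient among 55, scored as cleared, is enough to reach 8.1%.

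It would be tempting to read 46.0% as the trial's error rate, or to attribute the inflation to all three mismatches. The documents support neither: the figure needs five or six ineligible patients to pass review and all be scored as cleared, and only the N2 gap acts on the endpoint. This is worth correcting because the remedy is cheap and the primary rate depends on it. It does not show that the design itself is wrong; with N2 confirmed in every patient, the stated error and power hold.

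**What to change.** - **Appendix B, N2:** add a required item for pathologically confirmed N2 with station, method and date. In 3.1, change should to must for confirmed N2.
- **Section 18.1:** define clearance as negative N2 after treatment among patients with pathologically confirmed N2 at baseline.
- **Sections 18.1 and 18.5:** reconcile them. State whether a patient found ineligible after registration is counted, and if not, whether that patient is replaced so that the boundaries still apply to 19 and 55.
- **Appendix B, exclusions:** carry the missing 3.2 exclusions onto the form in their existing wording. The cardiac items are currently to be considered for exclusion; copying them as absolute bars would change the rule.
- **Diagnosis window:** 3.1 and Appendix B must be reconciled. Which window applies is for the study team to decide.
- **Staging reference:** the form points to Appendix E, which holds the case report forms; the staging table is in Appendix F.

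The cost is a form revision and a short amendment to 3.1, 18.1 and 18.5. Sample size, boundaries, visits and treatment are unchanged. Section 3.1 already expects baseline nodal confirmation, so added sampling should be limited to patients who would otherwise have been registered without it.

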10.0 PHARMACEUTICAL INFORMATION

10.1 Erlotinib (Tarceva®)

Chemical Name: Erlotinib is a quinazolinamine with the chemical name N-(3-ethynylphenyl)-6,7-bis(2-methoxyethoxy)-4-quinazolinamine. TARCEVA® contains erlotinib as the hydrochloride salt, which has the following structural formula:

Other Names: CP-358, 774, USAN: OSI-774 (Erlotinib) hydrochloride, Tarceva®

Classification: Signal Transduction Inhibitor, Tyrosine kinase Inhibitor (EGFR)

Molecular Formula: C₂₂H₂₃N₃O₄.HCl **Molecular Weight:** 429.90

Mode of Action:

The mechanism of clinical anti-tumor action of erlotinib is not fully characterized. Erlotinib inhibits the intracellular phosphorylation of tyrosine kinase associated with the epidermal growth factor receptor (EGFR). Specificity of inhibition with regard to other tyrosine kinase receptors has not been fully characterized. EGFR is expressed on the cell surface of normal cells and cancer cells.

How Supplied:

Erlotinib tablets are available in 25 mg, 100 mg and 150 mg erlotinib and contain the following inactive ingredients: lactose monohydrate, hypromellose, hydroxypropyl cellulose, magnesium stearate, microcrystalline cellulose, sodium starch glycolate, sodium lauryl sulfate and titanium dioxide. All tablets are round, white, film-coated bi-convex tablets without markings. Erlotinib hydrochloride, clinical trial material will be provided by Astellas, the study sponsor.

Storage:

The intact bottles should be stored at controlled room temperature 15°C-30°C- (59°F and 86°F). Tarceva® tablets are supplied in blue-white high-density polyethylene (HDPE) bottles of 30 each with some overage.

Route of Administration: Oral.

Method of Administration

Tarceva® tablets should be taken at approximately the same time each day. Each Tarceva® dose is to be taken with up to 200 mL (~ 1 cup or 8 oz) of water one hour before or two hours after meals or medications, including vitamins and iron supplements. Tarceva® should not be taken with grapefruit juice. The entire dose must be taken at one time. If the patient vomits after taking the tablet(s), the dose is replaced only if the tablet(s) can actually be seen and counted.

Warnings and Precautions**Interstitial Lung Disease (ILD):**

Cases of serious ILD, including fatal cases, can occur with TARCEVA treatment. The overall incidence of ILD in approximately 32,000 TARCEVA-treated patients in uncontrolled studies and studies with concurrent chemotherapy was approximately 1.1%. In patients with ILD, the onset of symptoms was between 5 days to more than 9 months (median 39 days) after initiating TARCEVA therapy. Withhold TARCEVA for acute onset of new or progressive unexplained pulmonary symptoms such as dyspnea, cough, and fever pending diagnostic evaluation. If ILD is confirmed, permanently discontinue TARCEVA

Renal Failure

Hepatorenal syndrome, severe acute renal failure including fatal cases, and renal insufficiency can occur with TARCEVA treatment. Renal failure may arise from exacerbation of underlying baseline hepatic impairment or severe dehydration. The pooled incidence of severe renal impairment in the 3 monotherapy lung cancer studies was 0.5% in the TARCEVA arms and 0.8% in the control arms. The incidence of renal impairment in the pancreatic cancer study was 1.4% in the TARCEVA plus gemcitabine arm and 0.4% in the control arm. Withhold TARCEVA in patients developing severe renal impairment until renal toxicity is resolved. Perform periodic monitoring of renal function and serum electrolytes during TARCEVA treatment.

Hepatotoxicity with or without Hepatic Impairment

Hepatic failure and hepatorenal syndrome, including fatal cases, can occur with TARCEVA treatment in patients with normal hepatic function; the risk of hepatic toxicity is increased in patients with baseline hepatic impairment. In clinical studies where patients with moderate to severe hepatic impairment were excluded,

the pooled incidence of hepatic failure in the 3 monotherapy lung cancer studies was 0.4% in the TARCEVA arms and 0% in the control arms. The incidence of hepatic failure in the pancreatic cancer study was 0.4% in the TARCEVA plus gemcitabine arm and 0.4% in the control arm. In a pharmacokinetic study in 15 patients with moderate hepatic impairment (Child-Pugh B) associated with significant liver tumor burden, 10 of these 15 patients died within 30 days of the last TARCEVA dose. One patient died from hepatorenal syndrome, 1 patient died from rapidly progressing liver failure and the remaining 8 patients died from progressive disease. Six out of the 10 patients who died had baseline total bilirubin > 3 x ULN.

Perform periodic liver testing (transaminases, bilirubin, and alkaline phosphatase) during treatment with TARCEVA. Increased frequency of monitoring of liver function is required for patients with pre-existing hepatic impairment or biliary obstruction. Withhold TARCEVA in patients without pre-existing hepatic impairment for total bilirubin levels greater than 3 times the upper limit of normal or transaminases greater than 5 times the upper limit of normal. Withhold TARCEVA in patients with pre-existing hepatic impairment or biliary obstruction for doubling of bilirubin or tripling of transaminases values over baseline. Discontinue TARCEVA in patients whose abnormal liver tests meeting the above criteria do not improve significantly or resolve within three weeks.

Gastrointestinal Perforation

Gastrointestinal perforation, including fatal cases, can occur with TARCEVA treatment. Patients receiving concomitant anti-angiogenic agents, corticosteroids, NSAIDs, or taxane-based chemotherapy, or who have prior history of peptic ulceration or diverticular disease may be at increased risk of perforation. The pooled incidence of gastrointestinal perforation in the 3 monotherapy lung cancer studies was 0.2% in the TARCEVA arms and 0.1% in the control arms. The incidence of gastrointestinal perforation in the pancreatic cancer study was 0.4% in the TARCEVA plus gemcitabine arm and 0% in the control arm. Permanently discontinue TARCEVA in patients who develop gastrointestinal perforation.

Bullous and Exfoliative Skin Disorders

Bullous, blistering and exfoliative skin conditions, including cases suggestive of Stevens-Johnson syndrome/Toxic epidermal necrolysis, which in some cases were fatal, can occur with TARCEVA treatment. The pooled incidence of bullous and exfoliative skin disorders in the 3 monotherapy lung cancer studies was 1.2% in the TARCEVA arms and 0% in the control arms. The incidence of bullous and exfoliative skin disorders in the pancreatic cancer study was 0.4% in the TARCEVA plus Gemcitabine arm and 0% in the control arm. Discontinue TARCEVA treatment if the patient develops severe bullous, blistering or exfoliating conditions.

Myocardial Infarction/Ischemia

In the pancreatic carcinoma trial, six patients (incidence of 2.1%) in the TARCEVA/gemcitabine group developed myocardial infarction/ischemia. One of these patients died due to myocardial infarction. In comparison, 3 patients in the placebo/gemcitabine group developed myocardial infarction (incidence 1.1%), and one died due to myocardial infarction. The pooled incidence of myocardial infarction/ischemia in the 3 monotherapy lung cancer studies was 0.2% in the TARCEVA arms and 0.4% in the control arms.

Cerebrovascular Accident

In the pancreatic carcinoma trial, seven patients in the TARCEVA/gemcitabine group developed cerebrovascular accidents (incidence: 2.5%). One of these was hemorrhagic and was the only fatal event. In comparison, in the placebo/gemcitabine group there were no cerebrovascular accidents. The pooled incidence of cerebrovascular accident in the 3 monotherapy lung cancer studies was 0.6% in the TARCEVA arms and 0.9% in the control arms.

Microangiopathic Hemolytic Anemia with Thrombocytopenia

The pooled incidence of microangiopathic hemolytic anemia with thrombocytopenia in the 3 monotherapy lung cancer studies was 0% in the TARCEVA arms and 0.1% in the control arms. The incidence of microangiopathic hemolytic anemia with thrombocytopenia in the pancreatic cancer study was 1.4% in the TARCEVA plus gemcitabine arm and 0% in the control arm.

Ocular Disorders

Corneal perforation or ulceration can occur with TARCEVA treatment. Other ocular disorders including abnormal eyelash growth, keratoconjunctivitis sicca or keratitis have been observed with TARCEVA treatment and are known risk factors for corneal ulceration/perforation. The pooled incidence of ocular disorders in the 3 monotherapy lung cancer studies was 17.8% in the TARCEVA arms and 4% in the control arms. The incidence of ocular disorders in the pancreatic cancer study was 12.8% in the TARCEVA plus gemcitabine arm and 11.4% in the control arm. Interrupt or discontinue TARCEVA therapy if patients present with acute/worsening ocular disorders such as eye pain

Hemorrhage in Patients Taking Warfarin

Severe and fatal hemorrhage associated with International Normalized Ratio (INR) elevations can occur when TARCEVA and warfarin are administered

concurrently. Regularly monitor prothrombin time and INR during TARCEVA treatment in patients taking warfarin or other coumarin-derivative anticoagulants

Embryo-Fetal Toxicity

Based on its mechanism of action, TARCEVA can cause fetal harm when administered to a pregnant woman. When given during organogenesis, erlotinib administration resulted in embryo-fetal lethality and abortion in rabbits at doses approximately 3 times the recommended human daily dose of 150 mg. If TARCEVA is used during pregnancy, or if the patient becomes pregnant while taking this drug, the patient should be apprised of the potential hazard to a fetus.

Advise females of reproductive potential to use highly effective contraception during therapy, and for at least 2 weeks after the last dose of TARCEVA. Advise patients to contact their healthcare provider if they become pregnant, or if pregnancy is suspected, while taking TARCEVA.

ADVERSE REACTIONS

The following serious adverse reactions, which may include fatalities, are discussed in greater detail above:

- Interstitial Lung Disease (ILD) Renal Failure
- Hepatotoxicity with or without Hepatic Impairment
- Gastrointestinal Perforation
- Bullous and Exfoliative Skin Disorders
- Myocardial Infarction/Ischemia
- Cerebrovascular Accident
- Microangiopathic Hemolytic Anemia with Thrombocytopenia
- Ocular Disorders
- Hemorrhage in Patients Taking Warfarin

Clinical Trial Experience

Because clinical trials are conducted under widely varying conditions, adverse reaction rates observed in the clinical trials of a drug cannot be directly compared to rates in the clinical trials of another drug and may not reflect the rates observed in practice.

Safety evaluation of TARCEVA is based on more than 1200 cancer patients who received TARCEVA as monotherapy, more than 300 patients who received TARCEVA 100 or 150 mg plus gemcitabine, and 1228 patients who received TARCEVA concurrently with other chemotherapies.

The most common adverse reactions with TARCEVA are rash and diarrhea usually with onset during the first month of treatment. The incidences of rash and

diarrhea from clinical studies of TARCEVA for the treatment of NSCLC and pancreatic cancer were 70% for rash and 42% for diarrhea.

Non-Small Cell Lung Cancer

First-Line Treatment of Patients with EGFR Mutations

The most frequent ($\geq 30\%$) adverse reactions in TARCEVA-treated patients were diarrhea, asthenia, rash, cough, dyspnea and decreased appetite. In TARCEVA-treated patients the median time to onset of rash was 15 days and the median time to onset of diarrhea was 32 days.

The most frequent Grade 3-4 adverse reactions in TARCEVA-treated patients were rash and diarrhea. Dose interruptions or reductions due to adverse reactions occurred in 37% of TARCEVA-treated patients, and 14.3% of TARCEVA treated patients discontinued therapy due to adverse reactions. In TARCEVA-treated patients, the most frequently reported adverse reactions leading to dose modification were rash (13%), diarrhea (10%), and asthenia (3.6%).

Selected, common adverse reactions in the study, occurring in at least 10% of patients who received TARCEVA or chemotherapy and an increase in $\geq 5\%$ in the TARCEVA treated group, are summarized by NCI-CTC (version 3.0) Grade in Table 1. The median duration of TARCEVA treatment was 9.6 months in the study 4.

Table 1: Selected Adverse Reactions with an Incidence Rate $\geq 10\%$ and an Increase of $\geq 5\%$ in the TARCEVA-treated Group

MedDRA Preferred Term	TARCEVA N = 84		Chemotherapy + N = 83	
	All Grades %	Grades 3-4 %	All Grades %	Grades 3-4 %
Rash †	85	14	2	0
Diarrhea	62	5	21	1
Cough	48	1	40	0
Dyspnea	45	8	30	4
Dry skin	21	1	2	0
Back pain	19	2	5	0
Chest pain	18	1	12	0
Conjunctivitis	18	0	0	0
Mucosal inflammation	18	1	6	0
Pruritus	16	0	1	0
Paronychia	14	0	0	0
Arthralgia	13	1	6	1
Musculoskeletal pain	11	1	1	0

DRUG INTERACTIONS

CYP3A4 Inhibitors

Erlotinib is metabolized predominantly by CYP3A4. Co-treatment with the potent CYP3A4 inhibitor ketoconazole increased erlotinib AUC by 67%. When TARCEVA was

co-administered with ciprofloxacin, an inhibitor of both CYP3A4 and CYP1A2, the erlotinib exposure [AUC] and maximum concentration [C_{max}] increased by 39% and 17%, respectively. Dose modifications are recommended.

CYP3A4 Inducers

Pre-treatment with the CYP3A4 inducer rifampicin for 7-11 days prior to TARCEVA decreased erlotinib AUC by 58% to 80%. Dose modifications are recommended

Drugs Affecting Gastric pH

Co-administration of TARCEVA with omeprazole decreased erlotinib AUC by 46% and co-administration of TARCEVA with ranitidine 300 mg decreased erlotinib AUC by 33%. When TARCEVA was administered with ranitidine 150 mg twice daily (at least 10 h after the previous ranitidine evening dose and 2 h before the ranitidine morning dose), erlotinib AUC decreased by 15%. Increasing the dose of TARCEVA when co-administered with such agents is not likely to compensate for the loss of exposure. Scheduling modifications are recommended

Cigarette Smoking

Cigarette smoking results in reductions in erlotinib AUC. Dose modifications are recommended

Anticoagulants

Interaction with coumarin-derived anticoagulants, including warfarin, leading to increased International Normalized Ratio (INR) and bleeding adverse reactions, which in some cases were fatal, have been reported in patients receiving TARCEVA. Regularly monitor prothrombin time or INR in patients taking coumarin-derived anticoagulants. Dose modifications of TARCEVA are not recommended

USE IN SPECIFIC POPULATIONS

Pregnancy

Pregnancy Category D

Risk Summary

Based on its mechanism of action, TARCEVA can cause fetal harm when administered to a pregnant woman. When given during organogenesis, erlotinib administration resulted in embryo-fetal lethality and abortion in rabbits at doses approximately 3 times the recommended human daily dose of 150 mg. If TARCEVA is used during pregnancy, or if the patient becomes pregnant while taking this drug, the patient should be apprised of the potential hazard to a fetus.

Animal Data

Erlotinib has been shown to cause maternal toxicity resulting in embryo-fetal lethality and abortion in rabbits when given during the period of organogenesis at doses that result in plasma drug concentrations approximately 3 times those achieved at the recommended dose in humans (AUCs at 150 mg daily dose). During the same period, there was no increase in the incidence of embryo-fetal lethality or abortion in rabbits or rats at doses resulting in exposures approximately equal to those in humans at the recommended daily dose. In an independent fertility study female rats treated with 30 mg/m²/day or 60 mg/m²/day (0.3 or 0.7 times the recommended daily dose, on a mg/m² basis) of erlotinib had an increase in early resorptions that resulted in a decrease in the number of live fetuses.

No teratogenic effects were observed in rabbits or rats dosed with erlotinib during organogenesis at doses up to 600 mg/m²/day in the rabbit (3 times the plasma drug concentration seen in humans at 150 mg/day) and up to 60 mg/m²/day in the rat (0.7 times the recommended dose of 150 mg/day on a mg/m² basis).

Nursing Mothers

It is not known whether erlotinib is present in human milk. Because many drugs are present in human milk and because of the potential for serious adverse reactions in nursing infants from TARCEVA, a decision should be made whether to discontinue nursing or discontinue the drug, taking into account the importance of the drug to the mother.

Pediatric Use

The safety and effectiveness of TARCEVA in pediatric patients have not been established.

Geriatric Use

Of the 1297 subjects in clinical studies of TARCEVA for the treatment of NSCLC and pancreatic cancer 40% were 65 and older while 10% were 75 and older. No overall differences in safety or efficacy were observed between subjects 65 years and older and those younger than 65.

Females and Males of Reproductive Potential

Contraception

Females

Counsel patients on pregnancy planning and prevention. Advise female patients of reproductive potential to use highly effective contraception during treatment with TARCEVA, and for at least 2 weeks after the last dose of TARCEVA. Advise patients to

contact their healthcare provider if they become pregnant, or if pregnancy is suspected, while taking TARCEVA.

Patients with Hepatic Impairment

Patients with hepatic impairment (total bilirubin > upper limit of normal (ULN) or Child-Pugh A, B and C) should be closely monitored during therapy with TARCEVA. Treatment with TARCEVA should be used with extra caution in patients with total bilirubin > 3 x ULN

In vitro and *in vivo* evidence suggest that erlotinib is cleared primarily by the liver. However, erlotinib exposure was similar in patients with moderately impaired hepatic function (Child-Pugh B) compared with patients with adequate hepatic function including patients with primary liver cancer or hepatic metastases.

Patients with Renal Impairment

Less than 9% of a single dose is excreted in the urine. No clinical studies have been conducted in patients with compromised renal function.

OVERDOSAGE

Single oral doses of TARCEVA up to 1,000 mg in healthy subjects and weekly doses up to 1,600 mg in cancer patients have been tolerated. Repeated twice-daily doses of 200 mg single-agent TARCEVA in healthy subjects were poorly tolerated after only a few days of dosing. Based on the data from these studies, an unacceptable incidence of severe adverse reactions, such as diarrhea, rash, and liver transaminase elevation, may occur above the recommended dose. In case of suspected overdose, TARCEVA should be withheld and symptomatic treatment instituted.

Availability:

Tarceva® (Erlotinib) is commercially available and is not currently approved for neoadjuvant treatment but it has indication for the first line of patients with metastatic non-small cell lung cancer (NSCLC) whose tumors have epidermal growth factor receptor (EGFR) exon 19 deletions or exon 21 (L858R) substitution mutations as detected by an FDA-approved test; as the maintenance treatment of patients with locally advanced or metastatic non-small cell lung cancer whose disease has not progressed after four cycles of platinum-based first-line chemotherapy and for the treatment of patients with locally advanced or metastatic non-small cell lung cancer after failure of at least one prior chemotherapy regimen. In the U.S., Tarceva® (Erlotinib) is marketed by both Genentech BioOncology and Astellas. Clinical trial material that is “commercial in nature” will be provided by Astellas

References

Investigator’s Brochure: OSI 774 (Erlotinib, Tarceva®) Edition 17, dated 21 Mar 2013.

11.0 AGENT ACCOUNTABILITY:

Agent Inventory Records – The investigator, or a responsible party designated by the investigator, must maintain a careful record of the inventory and disposition of all agents received from manufacturer using a Drug Accountability Record Form.

12.0 REGULATORY AND REPORTING REQUIREMENTS:

